7.1.2 Analysis details

The composite endpoints for phase 2 and phase 3 (section 3.5.1) will be summarized along with their single component by a binomial response rate at each time point (only the first event will be considered). The Clopper-Pearson method will be used to estimate the two-sided 95% CIs.

Primary analyses on time to composite endpoint(s) will be performed using the KM methodology and the one-

sided log-rank test will be used to test for differences between treatment groups. See section 4.1 for more details on time-to-event analysis and representation.

The primary endpoint of phase 2 will be assessed also in phase 3 as secondary analysis, and vice versa.

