### 4 STUDY DESIGN AND METHODOLOGY

#### 4.1 Phase 2 Study design

The study is designed for the investigational use of a CXCR1 and CXCR2 allosteric antagonist named Reparixin. It will involve 48 adult patients with severe COVID-19 pneumonia in accord with any of the following:

1. Age 18 to 90.

2. Confirmed COVID-19 diagnosis

3. At least one of the following: (1) Respiratory distress,  $RR \ge 30$  breaths/min without oxygen; (2) Partial arterial oxygen pressure (PaO2) / Fraction of inspiration O2 (FiO2) >100 <300mmHg (1mmHg = 0.133kPa).

4. Chest imaging confirms lung involvement and inflammation.

5. Inflammatory status as documented by at least one of the following: Lactate dehydrogenase (LDH) > normal range, C-reactive protein (CRP)  $\geq$  100mg/L or IL-6  $\geq$  40pg/mL, serum ferritin  $\geq$  900ng/mL, XDP >20mcg/mL.

Patients randomized to the active treatment will receive an oral dose of reparixin (1200 mg tablets TID) for 7 days. In case of improvement, treatment can be prolonged at discretion of the investigator up to a total of 21 days of treatment. Patients randomized to the both arms will be offered, in case of worsening (e.g. need of ICU and/or mechanical ventilation), a rescue medication based on their physicians' judgement, without any constrain from the sponsor.

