#### 4.2 Phase 3 Study design

In the phase 3 segment of this study, it is planned that patients will be randomized 2:1 to Reparixin or standard of care. Patients randomized to the control arm will be offered a rescue medication with the active treatment (Reparixin 1200 mg oral tablets TID) or Reparixin 2.772 mg/kg body weight/hour IV infusion, if the oral route is unfeasible for the clinical condition. The Phase 3 design will be reassessed and pending re-evaluation based on Phase 2 study results.

**Phase 2 Study Design and Methodology:** Randomized 2:1, controlled, multicentre clinical trial in 48 adult patients with severe COVID-19 pneumonia

**Phase 3 Study Design and Methodology:** Randomized 2:1, controlled, multicentre clinical trial in 111 adult patients with severe COVID-19 pneumonia, to be re-assessed based on Phase 2 results.

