#### **Dose and Route of Administration**

**IV infusion:** In the Phase 3, for patients randomized to the control arm who have worsened after 24hrs and within 14 days from randomization, Reparixin will be offered as rescue medication also as a continuous i.v. infusion into a central vein or dedicated peripherally inserted central catheter at a dose of 2.772 mg/kg body weight/hour for up to 7 days (120hrs).

The Reparixin solution for IV infusion will be provided by the Sponsor.

The dosing solution for infusion will be prepared at the designated Pharmacy or authorized location within each centre according to local guidelines for sterile re-consitution of i.v. injectable solutions. For each 750 mL dosing solution volume, the content of a Vial (250 mL) will be diluted with 500 mL of 0.9% sterile saline to dispense reparixin as 11.00 mg/mL solution. The dosing solution will be placed in a 1000 mL sterile empty Infusion Bag. Dosing solutions will be prepared and used within 72 hours from preparation, unless the site has more restrictive rules

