In the phase 3 segment of this study, it is planned that subjects will be randomized 2:1 to reparixin or standard of care. In case of worsening after the first 24hrs, subjects under the control arm will be offered a rescue medication with the active treatment (reparixin 1200 mg oral tablets TID) or reparixin 2.772 mg/kg body weight/hour IV infusion, if the oral route is unfeasible for the clinical condition. The phase 3 design will be reassessed and decided based on the results of the phase 2.

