3.5 Efficacy endpoints

3.5.1 Primary endpoints

- Primary Endpoint for phase 2: Composite endpoint of clinical events (the subject requires at least one of the following: supplemental oxygen requirement, invasive mechanical ventilation use, admission to ICU, and use of a rescue medication for any reason);
- Primary Endpoint for phase 3: Composite endpoint of death and clinical severe events (the subject dies or requires invasive mechanical ventilation use and/or admission to ICU).

3.5.2 Secondary Endpoints:

- Clinical severity score (a seven-category ordinal scale) at any available time point
- Dyspnea severity (Liker categorical scale and VAS continuous scale) at any available time point;
- Changes in body temperature at any available time point;
- Duration and quantity of supplemental oxygen treatment at any available time point;
- Incidence and duration of mechanical ventilation use at any available time point;
- Incidence of ICU admission need at any available time point;
- Lung damage extension changes from baseline (assessed by Chest CT or Rx) at any available time point;
- Change from baseline in lung exudation degree (assessed by Chest CT or Rx) at any available time point;
- PaO₂ at any available time point;
- SpO₂ at any available time point;
- Partial arteriolar oxygen pressure (PaO₂) to fraction of inspiration O₂ (FiO₂) ratio at any available time point;
- CRP at any available time point;
- Hs-CRP at any available time point;

3.5.3 Exploratory Endpoints (not mandatory):

- Cytokine profile at any available time point;

- Concentration of reparixin in serum over time;
- SARS-CoV-2 virologic counts at any available time point.

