Composite endpoint of phase 2 and Time to event (days)	
From ADDITIONAL INFORMATION form:
 
 • if “Has the patient been admitted to the ICU?” = “Yes”, then component1 = “Yes” and date of event1 = Date of Visit • if “Has the patient been admitted to the ICU?” = “No”, then component1 = “No” 
From PATIENT STATUS form:
 
 • if “Is the subject eligible to switch to rescue medication?” = “Yes”, then component2 = “Yes” and date of event2 = Rescue treatment start date 
 ○ If Rescue treatment start date is missing, then Date of Visit will be used • if “Is the subject eligible to switch to rescue medication?” = “No”, then component2 = “No” 
From ADDITIONAL INFORMATION and MECHANICAL VENTILATION forms:
 
 • If “Has the patient been mechanically ventilated?” = “Yes” and type = “Invasive mechanical ventilation”, then component3 = “Yes” and date of event3 = mechanical ventilation start date 
 ○ If mechanical ventilation start date is missing, then Date of Visit will be used • If “Has the patient been mechanically ventilated?” is not empty and type ≠ “Invasive mechanical ventilation”, then component3 = “No” 
From “Worsening based on PaO₂/FiO₂” (see above):
 
 • if a patient is classified as “Worsened”, then component4 = “Yes” and date of event4 = Date of Visit • if a patient is classified as not “Worsened” (excluding missing classification), then component4 = “No” 
The composite endpoint is equal to “Yes” if at least one post-baseline component (1-4) is equal to “Yes” and the date of event is the corresponding date of event. In case of more component equal to “Yes”, the first date will be used.
 
Otherwise, if all component (1-4) are equal to “No” the composite endpoint will set as “No”. The date of event will be last date where is known that all components are equal to “No”.
 
Time to composite endpoint (days) = Date of event - Date of randomization

Parameter	Derivation

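### Repeating the phase 2 composite in phase 3 with its rescue component tilts that secondary comparison towards reparixin, because phase 3 rescue is described only for controls

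*SAP*

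**What the plan says.** SAP 7.1.2, on the primary analyses, ends: "The primary endpoint of phase 2 will be assessed also in phase 3 as secondary analysis, and vice versa". The phase 2 composite (SAP 3.5.1) consists of supplemental oxygen requirement, invasive ventilation, ICU admission and "use of a rescue medication for any reason". SAP 9.1, Table 7, scores the rescue component from the CRF item "Is the subject eligible to switch to rescue medication" and dates it by "date of event2 = Rescue treatment start date", falling back on the visit date if that is missing. The oxygen component is derived as PaO2/FiO2 worsening. It and ICU admission are dated by the visit at which they are recorded. Invasive ventilation takes its own start date. The earliest date counts.

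The rescue rule differs by phase. For phase 2, Protocol 4.1 says: "Patients randomized to the both arms will be offered, in case of worsening (e.g. need of ICU and/or mechanical ventilation), a rescue medication". For phase 3, Protocol 4.2 says: "Patients randomized to the control arm will be offered a rescue medication with the active treatment". Protocol 6.3 restricts IV rescue to the same arm: "for patients randomized to the control arm who have worsened after 24hrs and within 14 days from randomization". The protocol summary and SAP section 3 (general design) also name controls only. Three places name no arm: the line on rescue medication that opens the protocol summary, Protocol 6.2 and Protocol 11.1. For phase 3 they mention no agent but reparixin, and 6.2 is the control-treatment section.

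**The concern.** A component that both arms can reach in phase 2 becomes, as phase 3 is written, one that is described for controls only. The repeated log-rank comparison then partly measures the rescue rule.

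- **Extra failures.** The trigger is open-ended worsening. A control scored on the rescue item before any ICU, ventilation or PaO2/FiO2 event has failed. No rescue is described for an equally ill reparixin patient.
- **Earlier dates.** Scheduled visits after Day 2 are Week 1, end of treatment and end of follow-up (SAP Table 1). An ICU admission on day 3 is dated day 3 in a control who starts rescue that day. In a reparixin patient it is dated at the Week 1 visit, about day 7. This holds even if rescue never adds a failure of its own.

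At stake is how a reader interprets the only like-for-like repeat of the phase 2 endpoint in phase 3. It could look positive with an inactive drug.

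**Working it through.** **The plan's own figure.** SAP 3.2 gives 109 events in 111 patients. With exponential medians of 2 and 4 days, 21 days of follow-up and 2:1 allocation: 37 × (1 − 0.5^(21/2)) + 74 × (1 − 0.5^(21/4)) = 109.0. Schoenfeld power at HR 0.5 is Φ(√(109 × 2/9) × ln 2 − 1.96) = Φ(3.411 − 1.96) = 92.7%, or 91.7% at the final boundary of 0.02151. The figure reproduces and is not in dispute.

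**Inputs from the documents.** Phase 3 adds 111 − 48 = 63 patients, 42 against 21. The control median for the phase 2 composite is 2 days (SAP Table 2); 4 days was run as a variant. The test is a one-sided log-rank.

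**Assumed inputs.** Threshold 0.025 one-sided, matching the two-sided 0.05 default in SAP 4.1; 28 days of observation; no drug effect; the rescue-only hazard, the share of visit-dated events and rescue uptake. The documents give no value for the last three. They also do not say whether the repeat uses the 63 new patients or all 111, so both were run.

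**Route 1, extra failures.** Let the control-only rescue hazard be f times the hazard λ of the other components. The control hazard is λ(1 + f), so the apparent HR is 1/(1 + f) with no drug effect. Approximate rejection is Φ(√(E × 2/9) × ln(1 + f) − 1.96). With E = 109 × 63/111 ≈ 62, √(62 × 2/9) = 3.71. For f = 0.25 this is Φ(3.71 × 0.223 − 1.96) = Φ(−1.13) = 0.129. Simulation gives less, because rescue starts only after 24 hours and many events occur before then. It used 8,000 runs per cell, with rescue possible from day 1 to day 14.

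| f | Apparent HR | Formula, 62 events | Simulated, 63 pts, median 2 d | 63 pts, 4 d | Pooled 111, 2 d | Pooled 111, 4 d |
|---|---|---|---|---|---|---|
| 0 | 1.00 | 0.025 | 0.034 | 0.034 | 0.026 | 0.031 |
| 0.05 | 0.95 | 0.038 | 0.041 | 0.051 | 0.038 | 0.037 |
| 0.10 | 0.91 | 0.054 | 0.050 | 0.056 | 0.044 | 0.048 |
| 0.25 | 0.80 | 0.129 | 0.085 | 0.108 | 0.064 | 0.085 |
| 0.50 | 0.67 | 0.325 | 0.180 | 0.236 | 0.127 | 0.166 |

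The pooled columns add 48 phase 2 patients (32 against 16) with rescue alike in both arms. The 14-day limit is stated for IV rescue only. Without it, f = 0.25 gives 0.083 and 0.113 in 63 patients.

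**Route 2, dating alone.** There are no rescue-only failures here. A share q of events takes the next visit date, and rescued controls take the true day. In 63 patients with every worsening control starting rescue, rejection is about 6-10% for q = 0.25 and 13-20% for q = 0.50, across the visit calendars tried. If half start rescue it is about 4-5% and 7-9%. At q = 0.75 with full uptake it exceeds 25%. With daily visits it returns to about 3%.

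**After the change.** With rescue left out and q = 0.50, rejection is 0.031-0.033 in 63 patients and 0.026-0.032 in 111.

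**Cost of the change.** Rescued controls stay at risk while taking reparixin. With true medians of 2 and 5 days, 63 patients and the full drug effect at once on rescue, power of this test is 92% without crossover. It is 84%, 74% and 61% for f = 0.10, 0.25 and 0.50.

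**The case against.** Phase 3 is provisional. SAP 4.7 requires a protocol amendment and an updated SAP before it starts, lists endpoint changes among the possible adaptations, and the opening of SAP section 7 promises to amend affected sections. This stands as a reason for low severity. It does not settle the point: the asymmetry is in the phase 3 design as now written, and no clause addresses this component.

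The components are shown by arm beside the composite (SAP 7.1.2, Protocol 9.4.2.5), and SAP 7.1.3.2 analyses death, invasive ventilation and ICU admission separately. That would reveal the tilt to a careful reader but would not correct the log-rank test.

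A reader might infer that reparixin patients can never score on rescue. The documents do not say so. SAP 5.4 tabulates switching to rescue by treatment, Table 7 needs an answer on all four components before the composite is negative, and rescue counts whatever the reason. If sites complete the item for both arms, route 1 shrinks. The only named triggers, ICU need and ventilation, also overlap with other components, so rescue-only failures may be few. The dating route survives that overlap.

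Counting rescue as failure is a recognised way to handle crossover, and removing it has a price. This stands, and is why the version with rescue should still be reported.

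**Conclusion.** The concern holds as a minor point about one secondary analysis. As written, the phase 3 repeat of the phase 2 composite favours reparixin by an amount the documents do not determine. With no drug effect, illustrative rejection is about 4-24% in 63 patients, or about 4-17% if all 111 are pooled, against about 3%. This covers f from 0.05 to 0.50, or 25-50% of events visit-dated with half or all worsening controls starting rescue. The direction follows from the text; the size rests on assumed inputs.

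Two stronger readings are not supported. A reader might infer that the superiority claim is at risk. It is not: the claim needs both primary hypotheses rejected (SAP 7.1.1.2), and the phase 3 primary endpoint has no rescue component. A reader might also take this repeat as the test that confirms phase 2. The SAP confirms phase 2 through the severe composite, so the percentages above are not error rates for any trial conclusion.

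**What to change.** In SAP 7.1.2 and Table 7, in the update already due before phase 3:

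1. Base the phase 3 between-arm test of this composite on PaO2/FiO2 worsening, invasive ventilation and ICU admission, without rescue, by assigned arm.
2. Report the composite with rescue alongside it, descriptively.
3. Date ICU events by the admission date that Table 7 already uses for time to ICU. PaO2/FiO2 events stay visit-dated, but then alike in both arms.

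This is SAP wording only. The phase 3 rescue rule and primary endpoint stay as they are. Dating ICU by admission has no evident downside. Leaving rescue out has two: the tested version is no longer identical to the phase 2 composite, and crossover dilutes the contrast, with the worst-case power loss shown above. An alternative is to define and record need for rescue by identical criteria in both arms. That keeps the composite intact but requires a rule the documents do not yet contain.

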7.1.3 Sensitivity analysis

7.1.3.1 Phase 2

Results of primary analysis will be assessed in sensitivity analyses as detailed below.

- The comparison between treatment and control will be performed by means of a Cox regression model, using age class, gender and clinical severity score at baseline as covariates, to assess the robustness of results on primary endpoint versus the presence of confounding factors. Additional covariates might be included after DRM in case relevant baseline imbalance will be identified between groups, despite randomization. The assumptions of proportionality will be investigated with a time-dependent exploratory variable, which is defined as $\text{treatment} * \{\log[\text{time to event}]\}$. If the p-value from the Wald Chi-squared statistic for this variable is less than 5% there is evidence of a departure from the adjusted model assumptions. In case of non-proportional hazards, a Weibull model will be assumed as parametric form of the distribution of survival times. The treatment group will be included in the model as covariate.
- Time to event for each single component of the primary endpoint will be performed separately in order to adjust for the presence of possible competing risks. The following events:
 - first supplemental oxygen requirement,
 - first mechanical ventilation use,
 - first admission to ICU, and
 - first use of a rescue medication for any reason

will be analyzed according to survival analysis methodology detailed in section 4.1 with the following modifications:

- the common representation of survival curves using the Kaplan-Meier estimator will be replaced by the cumulative incidence function,
- the presence of other competing event(s) is/are treated as censored.
- A modified composite endpoint of phase 2 will be analyzed adding “death” as fifth component. It will be analyzed according to section 7.1.2 to assess the robustness of results on primary endpoint versus the presence of censoring due to fatal events.

Decision to proceed/not proceed to phase 3 will be based only on primary analysis results, despite inconsistencies with sensitivity analyses. Sensitivity results will be interpreted and discussed in the clinical study report and will be used to eventually adjust adaptations for the phase 3.

7.1.3.2 Phase 3

Results of primary analysis will be assessed in sensitivity analyses as detailed below.

- The comparison between treatment and control will be performed by means of a regression model, using the same method (Cox or Weibull model) and covariates identified during phase 2, to assess the robustness of results on primary endpoint versus the presence of confounding factors.
- Time to event for each single component of the severe primary endpoint will be performed separately in order to adjust for the presence of possible competing risks. The following events:
 - death,
 - first invasive mechanical ventilation use, and
 - first admission to ICU

will be analyzed according to survival analysis methodology detailed in section 4.1 with the following modifications:

- the common representation of survival curves using the Kaplan-Meier estimator will be replaced by the cumulative incidence function,
- the presence of other competing event(s) is/are treated as censored.
- The comparison between treatment and control will be performed in the PP population instead of FAS as described in section 7.1.2, to assess the robustness of trial results versus the adherence to protocol.

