## 9.4.2.4 Sensitivity analyses

The following sensitivity analyses are defined to assess the robustness of results on primary endpoints versus adherence to protocol and presence of confouring factors:

Comparison between treatment and control will be performed in the PP population (see section 9.3 for definition) instad of FAS;

Comparison between treatment and control will be performed by means of a Cox regression model, using pre-specified baseline charateristics as covariates (details will be provided in the SAP). The above sensistivity assessemnts will be performed at the time of phase III analysis. Additional sensitivity analyses may be added in the SAP.

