3.3 Randomization and blinding

Eligible subjects will be randomized in a 2:1 fashion to either reparixin or standard of care through an Interactive Response System (IRS).

Randomization will be stratified by site to ensure balanced assignment across treatment groups. A stratified permuted block randomization list will be generated with a computer procedure, randomizing an excess of subjects to allow competitive recruitment within each center. Each randomized subject will be allocated with randomization number according to the stratified randomization list.

Given the open-label nature of the trial and the stratification by site, random block sizes will be adopted in the randomization list to avoid that treatment assignments might be forecasted by investigators.

The master randomization list will be kept confidential and will not be disclosed to any other person than those for which is strictly required (i.e. independent statistician who create the list, and IRS provider personnel).

Mis-randomization events will be recorded as major deviation and reported in the final study report.

Randomization codes will not be reused in case of subject's dropouts.

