4.4 Sub-group analyses

Statistical tests for interaction (between subgroup and treatment arm) will be performed to decide about the need to further investigate subgroups of the trial population. The consistency of the treatment effect will be assessed using a Cox regression model including treatment, subgroup variable and their interaction as covariate.

The following subgroups will be defined based on demographic or baseline characteristics:

- age group (≤ 65 yrs vs > 65 yrs);
- gender (Male, Female);
- clinical severity score at baseline ($<$ median vs \geq median);
- dyspnea VAS scale at baseline ($<$ median vs \geq median).

Subgroup analysis will be performed if interaction tests are statistically significant at 15% nominal level. In this case all efficacy endpoints will be analyzed within as described in sections 7.1.2, 7.2.1 and 7.2.2.

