4.10 Data Review Meeting

A DRM will be held before final database lock.

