9.1 Variable derivation

Table 7: Variable derivation rules

Parameter	Derivation
ARDS Severity classification based on PaO₂/FiO₂	
According to PaO₂/FiO₂ (RESPIRATORY PARAMETERS form) the classification is:
 
 • if $200 \leq \text{PaO}_2/\text{FiO}_2 < 300$ mmHg then ARDS Severity=Mild • if $100 \leq \text{PaO}_2/\text{FiO}_2 < 200$ mmHg then ARDS Severity=Moderate • if $\text{PaO}_2/\text{FiO}_2 < 100$ mmHg then ARDS Severity=Severe
Worsening based on PaO₂/FiO₂	
A patient with ARDS ($\text{PaO}_2/\text{FiO}_2 < 300$ mmHg) is considered “Worsened” in case of a decrease of PaO₂/FiO₂ of at least one third (-33,3%) from the baseline PaO₂/FiO₂ value.

Oxygen Delivery System Classification based on type of oxygen support	
According to Type of oxygen support (RESPIRATORY PARAMETERS form) the classification is:
 
 • If “Invasive Medicinal Ventilation” or “ECMO” then Class=Invasive • Else if “High Flow Nasal Cannula” or “BIPAP or CPAP” then Class=High Flow • Else if “Nasal Cannula” or “Mask” then Class=Low Flow
Worsening based on Oxygen Delivery System Classification	
A patient is considered “Worsened” after baseline if he/she increase the level of severity within the oxygen delivery system classification (Invasive > High Flow > Low Flow).

Last available date (for censoring time-to-event analysis)	
Last date will be considered as the most recent dates collect in:
 
 • Last assessment, • Start and stop dates of AEs 
Last date = max (date of last assessment, start AEs, Stop AEs)

Parameter	Derivation

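### The adjusted Cox sensitivity model should have a covariate list fixed in advance, with age defined and baseline PaO2/FiO2 included; as written, the list can be extended at discretion after between-group imbalance is seen

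*SAP*

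**What the plan says.** Protocol 9.4.2.4 plans a Cox model "using pre-specified baseline charateristics as covariates (details will be provided in the SAP"). SAP 7.1.3.1 supplies the list for phase 2, "using age class, gender and clinical severity score at baseline as covariates", and then leaves it open: "Additional covariates might be included after DRM in case relevant baseline imbalance will be identified between groups". It gives no threshold for a relevant imbalance, no candidate variables and no labelling rule. SAP 7.1.3.2 has phase 3 proceed "using the same method (Cox or Weibull model) and covariates identified during phase 2".

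Age class has no definition in 7.1.3.1. The only age cut in the SAP is the subgroup variable of section 4.4, "age group (≤ 65 yrs vs > 65 yrs").

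In SAP 9.1, Table 7, the oxygen component of the phase 2 composite (component 4) is a decrease in PaO2/FiO2 "of at least one third (-33,3%) from the baseline" value. PaO2 and FiO2 are scheduled at screening and baseline (SAP Table 1), and the ratio is summarised as a baseline characteristic (SAP 5.8).

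On timing, SAP 4.10 says "A DRM will be held before final database lock", and SAP 3.3 describes its randomisation safeguards as "Given the open-label nature of the trial". SAP 7.1.2 makes the one-sided log-rank test primary, and 7.1.3.1 rests the phase 3 decision on that test alone. It also says that sensitivity results may inform phase 3 adaptations.

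**The concern.** The stated purpose of this model is to show that the primary result is robust to confounding. Three features limit how well it can do that.

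- **Open list.** Finding an imbalance between groups requires knowing allocation, and the trial is open label. If someone can then decide whether to add a variable, the adjusted estimate depends on a choice made with the data in view. That departs from the protocol's own requirement, although SAP 4.9 reports no change to the planned analysis.
- **Missing covariate.** A baseline PaO2/FiO2 that is high by chance makes a later one-third fall more likely without any true change. The model does not adjust for the value against which the event is defined.
- **Undefined age class.** A reader cannot tell which cut will be used, and any two-way cut discards information about age.

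At stake are the credibility and sensitivity of the adjusted analysis in phase 2, and its reuse in phase 3.

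**Working it through.** **1. The plan's own figure.** Inputs from SAP 3.2 and 4.5: 46 events, 2:1 allocation, median 2 versus 5 days (HR 2/5 = 0.40 under the exponential model), one-sided 0.025, one interim at 23 events. Schoenfeld's formula: sqrt(46 × 1/3 × 2/3) × |ln 0.40| − 1.960 = 3.197 × 0.916 − 1.960 = 0.97, so power is 83.4%. Simulating the SAP Table 4 boundaries gives 80.2% with the futility rule applied and 83.2% with it ignored. The stated figure of about 80% reproduces. It belongs to the unadjusted log-rank test, so no change of covariates affects it.

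**2. Dependence of component 4 on baseline.** The documents give no measurement variability, so it is assumed. With a within-patient SD of 0.20 on the log scale and no true change, the threshold is ln(2/3) = −0.405. If the measured baseline is 1 SD too high, the chance of a recorded one-third fall at one visit is Φ((0.20 − 0.405)/0.20) = Φ(−1.03) = 15%. If it is 1 SD too low, the chance is Φ((−0.20 − 0.405)/0.20) = Φ(−3.03) = 0.1%. A second calculation let true values be uniform over 100-300 mmHg:

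| Assumed CV | Baseline 100-150 | Baseline 250-300 |
|---|---|---|
| 0.10 | 0.1% | 0.2% |
| 0.15 | 1.1% | 3.3% |
| 0.20 | 3.0% | 9.6% |
| 0.30 | 6.4% | 22.6% |

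The dependence is present throughout. Its size depends on the assumed noise.

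**3. Age in two classes.** For normally distributed age, the information kept by a cut at 65 is φ(c)²/[p(1−p)], with c = (65 − mean)/SD and p = 1 − Φ(c). For assumed means of 55-70 and SDs of 10-15 years this is 44% to 64%.

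**4. How often the trigger is available.** With 32 versus 16 patients, the SE of a standardised difference is sqrt(1/32 + 1/16) = 0.306. The chance that one covariate differs by more than 0.25 SD is 2[1 − Φ(0.25/0.306)] = 41%.

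**5. Power of the adjusted model.** Cox simulation with 32:16 patients, exponential times, 21-day censoring, conditional HR 0.40, one-sided Wald test at 0.025 and 4,000 runs per row. The prognostic strengths are assumed. The fixed list has continuous age, gender, severity score and PaO2/FiO2.

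| Log-HR per SD: age / PaO2/FiO2 | SAP list | Fixed list | Change (points) |
|---|---|---|---|
| 0 / 0 | 80.2% | 79.2% | −1.0 |
| 0.2 / 0.25 | 76.9% | 79.2% | +2.3 |
| 0.4 / 0.25 | 73.8% | 78.5% | +4.7 |
| 0.2 / 0.5 | 69.7% | 78.4% | +8.7 |
| 0.4 / 0.5 | 67.8% | 77.7% | +9.9 |
| 0.4 / 0.75 | 59.7% | 76.5% | +16.8 |

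Simulation error is about sqrt(0.8 × 0.2/4000) = 0.6 points per entry. The gain does not come from precision: the mean SE rises from 0.36 to 0.37-0.38. It comes from a larger estimated conditional log-HR (last row: −0.80 to −1.01).

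**6. Type I error of the adjusted model.** Same set-up with HR 1, nominal 2.5%. SAP list: 3.4-3.7% (small-sample Wald test). Adding PaO2/FiO2 mechanically whenever it is imbalanced: 3.2-4.0%. Reporting the most favourable of the unadjusted model, the SAP model and the SAP model plus PaO2/FiO2: 5.2-6.8%.

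**7. Cost in parameters.** With the severity score as one term, events per parameter go from 46/4 = 11.5 to 46/5 = 9.2. With the score as three terms they go from 46/6 = 7.7 to 46/7 = 6.6.

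**The case against.** The strongest reply is that this is a sensitivity analysis with no alpha, boundary or power target, and that the SAP states that sensitivity results do not govern entry to phase 3. That stands, and it sets the weight of the point. Other parts of the reply also stand:

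- The severity score grades oxygen support, so baseline respiratory status is partly adjusted for already. When the score was assumed to correlate 0.8 with PaO2/FiO2, a separate simulation of the two lists gave 74% to 80% with weaker assumed effects and 61% to 76% with stronger ones. It gave about 1-2 points with no PaO2/FiO2 effect.
- Coupling makes a high baseline raise event risk, whereas disease severity may make a low one do so. A linear term could misfit, so its form needs thought.
- Under randomisation, noise in the baseline value adds event noise. It does not bias the comparison.
- The trigger for adding covariates is baseline data, not outcome, and SAP 4.1 requires unplanned analyses and deviations to be documented.
- PaO2/FiO2 is one of two alternative entry routes, is measured by local procedures, and may be missing. The SAP has no rule for missing covariates.

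The reply does not answer the conflict with the protocol. A named base list does not make the final list pre-specified when additions are discretionary and carry into phase 3.

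**Conclusion.** The point holds as a low-cost improvement to a secondary part of the plan. The open list, its conflict with the protocol, the undefined age class and the absence of baseline PaO2/FiO2 can all be read directly from the text. The sizes rest on assumptions: −1 to +17 points of power in the adjusted model, with conditional HR 0.40 and prognostic strengths the documents do not give; and type I error of about 5-7% only if the most favourable of three models is reported.

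A reader might infer more than the documents support:

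- **That the trial gains power at no cost.** The primary test is untouched, the change is slightly negative if the covariates are not prognostic, and one parameter is spent. A gain of 9-24 points appears only when a model with treatment and age class alone is the comparator, under strong assumed effects. That is not the SAP's list.
- **That the adjusted analysis is unusable.** A mechanical imbalance rule leaves type I error essentially where it was. The exposure comes from discretion.
- **That the SAP cuts age at 65 in this model.** That is inferred from the subgroup section.
- **That the DRM is an unblinded look at outcomes.** The SAP does not say so. Only knowledge of allocation for baseline data is implied.
- **That the coupling argument applies to phase 3.** The phase 3 composite in Table 7 has no PaO2/FiO2 component.

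**What to change.** In SAP 7.1.3.1, before any between-group look, set the list as age (continuous), gender, baseline clinical severity score and baseline PaO2/FiO2. State the functional form of PaO2/FiO2 (for example log) and the rule for a missing baseline value; the screening measurement is one available candidate. State whether the severity score enters as one term or by category.

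Replace the sentence on post-DRM additions with one that labels any such model post hoc and reports it beside the pre-specified model. In SAP 7.1.3.2, replace the inherited list with one fixed in advance and justified for the phase 3 endpoint.

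The cost is SAP wording and one extra parameter with about 46 events. The measurements are already scheduled, and no additional patients or visits are needed.
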